Relationship between attention and emotional function after traumatic brain injury (TBI): probing neural circuitry with transcranial direct current stimulation (tDCS)

I. PURPOSE OF THE STUDY AND BACKGROUND

1. Purpose of the study

The purpose of this pilot study is to investigate the relationship between attention and emotional function post-TBI in an effort to better understand the cognitive mechanisms of emotional processing in patients with TBI, and explore novel treatment strategies to improve emotional regulation using tDCS to modulate activity in the dysfunctional prefrontal-limbic circuits. This project will provide pilot data for extramural funding to expand on this topic.

The specific aims are:

1) To examine the relationship between alerting, orienting and executive attention and emotional recognition, reactivity and regulation in patients with TBI and controls.

Hypothesis: Patients with TBI will show clear patterns of attentional and emotional impairment compared with controls. Deficits in executive attention will be related to deficits in emotional appraisal in patients.

2) To determine whether anodal tDCS applied over the dorsolateral prefrontal cortex in conjunction with computer assisted cognitive re-training of attention will lead to greater improvement in attention and/or emotional regulation compared with sham-tDCS + cognitive re-training. Hypothesis: Patients receiving tDCS + cognitive re-training will show greater improvement in post-intervention measures of attention and emotional regulation.

3) To determine whether resting-state activation patterns in the fronto-limbic connections of patients receiving tDCS + cognitive re-training show greater improvement compared with sham-tDCS + cognitive re-training, using functional connectivity MRI (fMRI).

Hypothesis: Patients receiving tDCS + cognitive re-training will show higher temporal correlation between the frontal and limbic areas compared to baseline than patients receiving sham tDCS + cognitive re-training.

2. Background and Significance

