2.2 Diffuse Axonal Injury (DAI) leads to shearing of limbic-prefrontal circuits

TBI is caused by rapid acceleration-deceleration of the brain inside the skull, which causes DAI, or disruption of axonal connections between widespread regions of the brain. However, the extent of DAI is difficult to quantify (Inglese, Makani et al. 2005) as it requires sophisticated imaging techniques that are not widely available (Cohen, Inglese et al. 2007). Realistic in vivo and in vitro models of TBI have been able to demonstrate that DAI, marked by bead-like pattern of beta-amyloid precursor protein (beta-APP) in damaged axons, leads to early degeneration particularly in axons of the cingulum bundle and external capsule leading to disconnection between the cortical and thalamic neurons with delayed apoptotic death in the nuclei of the limbic cortex, the seat of emotions (Dikranian, Cohen et al. 2008; Kilbourne, Kuehn et al. 2009). Similarly, a functional magnetic resonance imaging (fMRI) study that compared patterns of cortical activation in patients with cognitive impairment after TBI and controls during a Stroop task, showed that TBI patients showed decreased activity in the anterior cingulate cortex which may reflect cortical disinhibition attributable to disconnection or compensation for an inefficient cognitive process (Soeda, Nakashima et al. 2005). Many of the behavioral symptoms of TBI such as prominent impulsivity, affective instability, disinhibition, difficulties with substance use, sexual expression, and aggression (McAllister 1992) stem from perseverative behavior that can be explained by damage to the prefrontal cortex and/or disconnection between limbic and prefrontal circuits (Morgan, Romanski et al. 1993; Neave, Nagle et al. 1997; Sotres-Bayon, Cain et al. 2006; Hartley and Phelps 2010). Detailed electrophysiologic and functional neuroimaging studies on the emotion of fear have revealed that interactions between the amygdala and hippocampus in the limbic system and the ventromedial prefrontal cortex (VMPFC) and dorsolateral prefrontal cortex (DLPFC) support the acquisition, storage, retrieval, and regulation of emotional memory (Sotres-Bayon, Cain et al. 2006; Hartley and Phelps 2010).

2.3 Stimulation of dorsolateral prefrontal cortex (DLPFC) and prefrontal-limbic circuit plasticity

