A primary goal of cognitive therapy is to enable the patient to more accurately assess a situation, using cognitive strategies such as emotional reappraisal, selective attention and reframing (Gross 1998; Gross and John 1998), in order to regulate the associated emotional responses (Allen, McHugh et al. 2008). In turn, successful treatment of emotional dysregulation (altering the emotional response) after TBI involves the employment of cognitive strategies that require the patient's active engagement and cognitive reappraisal of the event (Olsson and Ochsner 2008; Macnamara, Ochsner et al. 2010). Functional neuroimaging studies on reappraisal of negative affect have consistently reported increased activation of the DLPFC and/or VLPFC and decreased amygdala activation (Wager, Davidson et al. 2008; Ochsner, Hughes et al. 2009; McRae, Hughes et al. 2010). The cognitive regulation of emotion model (Ochsner, Bunge et al. 2002; Delgado, Nearing et al. 2008; Schiller and Delgado 2010) proposes that the DLPFC is involved in the effortful manipulation or interpretation of the emotional stimulus and the VLPFC may have a function in the selection of emotional interpretation (Wager, Davidson et al. 2008). The changes observed in the amygdala are thought to result from top-down modulation of the emotional meaning of the stimulus.

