2.4 We will use resting state functional connectivity MRI (fMRI) to directly test the hypothesis that tDCS strengthens fronto-limbic connections involved in emotional processing. Resting state functional connectivity MRI (fMRI) is a recently evolving method from which functional connectivity between distant brain regions is extracted based on low-frequency fluctuations. It allows for the identification of discrete functional networks in the brain. Distributed networks of brains regions have been shown to display temporally correlated patterns of spontaneous activation. This temporal coherence tends to occur in the brain regions that are anatomically connected (Zhang and Raichle 2010). Furthermore, functionally connected networks derived using resting state approaches mirror activation patterns found in task-based functional imaging studies. For clinical purposes, the strength and nature of network connections can be compared in clinical and healthy populations, or resting state can be used in a repeated measures fashion to assess changes within clinical groups. Resting state fMRI had been employed in a small number of studies of TBI patients to examine how network connectivity changes with recovery (Nakamura, Hillary et al. 2009; Hillary, Slocomb et al. 2011).

3. Study Design.

Forty (40) individuals status post TBI with complaints of emotional dysfunction 6 months post-brain injury and twenty-five (25) healthy controls will participate in the study. We expect a

total of 65 subjects to enroll. After obtaining informed consent, they will be screened to ensure that they meet inclusion-exclusion criteria at Visit 1. At visit 1 subjects also will be tested on chemosensory performance evaluation using Sniffin' sticks test and oculomotor movement evaluation using King-Devick test Subjects meeting criteria will then be tested at baseline on neuropsychological assessments, tests of attention (at Visit 2), and the emotional function battery (at Visit 3). The TBI subjects will also undergo resting-state MRI (at Visit 4).

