3) To determine whether the tDCS intervention produces stronger functional connectivity between fronto-limbic networks compared with sham-tDCS. Hypothesis: Patients receiving tDCS + cognitive re-training will show higher temporal correlation between the frontal and limbic areas compared to baseline than patients receiving sham tDCS + cognitive re-training.

Analyses of the resting state fMRI images will be performed using AFNI and FSL software packages (www.fmrib.ox.ac.uk/fsl/) using standard procedures. The images will be slice-time corrected, despiked, and motion corrected using AFNI, and time series detrending will be performed. The Brain Extraction Tool (Smith 2002; Smith, Jenkinson et al. 2004; Woolrich, Jbabdi et al. 2009) (BET) will be used to skull strip the images, which will be spatially smoothed using a Gaussian kernel. In the first stage analysis, data from each subject will be individually modeled. The stimulus time course will be convolved with a gamma function and the general linear model (GLM) will be employed with motion parameters as covariates. Additionally we will use temporal bandpass filtering (0.01 Hz < f < 0.1Hz), regression of the six motion parameters and of white matter and cerebrospinal fluid signals. Average resting state time series will be obtained for all the seeds of interest, particularly in the **cingulate motor cortex, and dorsolateral premotor cortex** based on prior studies.(Marshall, Zarahn et al. 2009) FSL FEAT will be employed to find the brain voxels that correlate with the seed time series in each subject. Individual functional connectivity maps will be registered to the MNI space and entered into group-level analyses. Higher level analyses will be carried out using FEAT. Connectivity patterns pre- and post-treatment will be compared for all the seeds of interest. Gaussian random field theory will be used for cluster-level multiple comparisons correction (minimum $Z > 2.3$; $p < .05$, corrected) for the resting state analyses.

Data Monitoring: The PI will be overall responsible for data monitoring.

(1) Types of Data or Events: All accumulated outcome data, enrollment numbers, reportable event data (including adverse reactions and unanticipated problems) and overall compliance with the protocol will be monitored.

(2) Responsibilities and roles for gathering, evaluating, and monitoring the data: The PI will be responsible for monitoring the data collected, including data related to adverse events and

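### The only seeds named for the Aim 3 connectivity analysis are motor and premotor regions, a poor match to its fronto-limbic hypothesis and left DLPFC stimulation; a stimulus term is also left in a resting-scan model

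*Protocol*

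**What the plan says.** Specific aim 3 (Protocol I.1), repeated under III.2 Data Analysis, item 3, states the hypothesis: "Patients receiving tDCS + cognitive re-training will show higher temporal correlation between the frontal and limbic areas compared to baseline", and more so than with sham. Section I.2.4 says that the scan is there to "directly test the hypothesis that tDCS strengthens fronto-limbic connections involved in emotional processing". It explains that with this method "functional connectivity between distant brain regions is extracted based on low-frequency fluctuations", and that brain networks show "temporally correlated patterns of spontaneous activation".

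The background describes the circuit of interest. Section I.2.2 centres on the amygdala and hippocampus interacting with the ventromedial prefrontal cortex (VMPFC) and DLPFC, and also reports "decreased activity in the anterior cingulate cortex" after TBI. Section I.2.3 cites imaging work on reappraisal that found "increased activation of the DLPFC and/or VLPFC and decreased amygdala activation". Section III.1.5 places the anode over F3 and makes the left DLPFC the focus of the study.

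The analysis in III.2, item 3, takes time series from an open list of seeds but singles out "cingulate motor cortex, and dorsolateral premotor cortex". It then produces seed-to-voxel maps and compares them before and after treatment. Its first-level model convolves a stimulus time course with a gamma function inside a general linear model (GLM) with motion covariates. Section III.1.4 describes the scan as taken at rest, eyes closed and without movement.

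**The concern.** The hypothesis, the purpose of the scan, the rationale and the stimulated site all point to prefrontal-limbic coupling. The analysis points to motor and premotor cortex. An analyst who followed the named seeds would obtain maps of what correlates with motor-related regions. Those maps do not directly answer whether the stimulated DLPFC changed its coupling with limbic areas. Because the pilot is meant to support later funding, Aim 3 could end with imaging results that bear only indirectly on the mechanism proposed.

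The stimulus term is a smaller matter. Read literally, that step has no input, because a resting scan supplies no stimulus timing.

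**Working it through.** The Protocol gives no figure to reproduce for this point, so the check sets its statements side by side.

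**Seeds**

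| Element | Where | Region |
|---|---|---|
| Hypothesis | I.1 aim 3; III.2 item 3 | frontal and limbic areas |
| Purpose of scan | I.2.4 | fronto-limbic connections |
| Circuit in the rationale | I.2.2, I.2.3 | amygdala, hippocampus, VMPFC, DLPFC, VLPFC; anterior cingulate also mentioned |
| Stimulated site | III.1.5 | left DLPFC |
| Seeds named | III.2 item 3 | cingulate motor, dorsolateral premotor |

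1. Two seeds are named. None is DLPFC, VMPFC, VLPFC, amygdala or hippocampus.
2. Neither named seed region appears anywhere else in the Protocol.
3. The one source cited for the seeds is, by its title in the reference list, an imaging study of motor recovery after stroke. This trial excludes people with prior stroke and people with focal upper-extremity motor deficits (II.6). The source itself was not available, so this step rests on the title alone.
4. The nearest link is the cingulate. Besides the mention in I.2.2, the description of the ANT-R in III.1.1 ties executive attention to the anterior cingulate. The Protocol nowhere connects the cingulate motor area with emotion.

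**Stimulus term**

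1. One modelling step calls for a stimulus time course. Section III.1.4 describes no stimulus or task in the scanner.
2. The film clips and startle probes cannot be the stimulus meant. Section I.3 puts the emotional battery at Visit 3 and the MRI at Visit 4.
3. The remaining steps form a workable resting-state analysis: band-pass filtering, regression of motion, white matter and cerebrospinal fluid signals, and correlation with the seed series.
4. The sentence with the convolution is also the only place where the GLM is mentioned. Deleting the whole sentence would remove the GLM as well.

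**The case against.** The strongest reply is that the seed list is not closed. The wording marks the two regions as particular cases among all seeds of interest, and it sits directly under a fronto-limbic objective. The maps are whole-brain. Dorsolateral premotor cortex is itself frontal, and the hypothesis speaks of frontal and limbic areas in general. An active-versus-sham change between that seed and a limbic cluster would fit the hypothesis as worded. All of this stands, and it limits the point to a poor match.

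A second reply is that seed coordinates, target regions and a primary pair are commonly fixed in an analysis plan, which is not shown here. That also stands: the lack of a final region list is not a fault in itself. It does not answer the point, which is about the regions that the Protocol does name.

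A reader might go further and infer that the regions are free to be picked after the maps are seen, or that false positives accumulate across seeds. The documents do not support either as a finding. The number of seeds is not given, and an analysis plan could fix the seeds or correct across them. Multiplicity is also a separate question, which would arise equally with well-chosen limbic seeds.

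**Conclusion.** The point holds as a mismatch between the stated analysis and the stated hypothesis. The named seeds represent neither the stimulated region nor the limbic side of the circuit, so they do not directly test the coupling that Aim 3 concerns. It would be too strong to say that Aim 3 cannot be tested or that limbic results are ruled out, because the open list and whole-brain maps leave both possible.

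The stimulus term is a minor wording error. A reader might take it to invalidate the imaging analysis, but the other steps stand without it.

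The sham comparison is not in question either: item 3 states it in both its objective and its hypothesis.

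The impact is limited to Aim 3 of a pilot whose sample size the Protocol itself calls arbitrary. It should be corrected. The conclusion rests on the Protocol's text and on no numerical assumption.

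**What to change.** In III.2 Data Analysis, item 3:

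1. Replace the named seeds with a left DLPFC seed and limbic target regions drawn from the Protocol's own rationale, for example amygdala and hippocampus. The investigators should set the final list before the maps are seen, since the background also mentions VMPFC, VLPFC and anterior cingulate. Label the cingulate motor and dorsolateral premotor seeds exploratory, or drop them.
2. Remove only the clause on convolving a stimulus time course. Keep the first-level GLM with the seed time series as its regressor, together with the motion, white matter and cerebrospinal fluid nuisance terms already stated.

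The cost is a change of wording in one section. The scans and software stay the same.

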1.5 Intervention with active and sham tDCS and computerized cognitive re-training

After providing informed consent approved by the IRB of New York University School of Medicine (NYUSoM), all patients will undergo testing with the above listed outcome measures. They will then be randomized into the two intervention groups, the groups being (1) tDCS + cognitive re-training, and (2) sham tDCS + cognitive re-training. The intervention will be carried out for 20 minutes twice a week for 6 weeks during which the subjects in each group will be engaged in re-training using visual cognitive re-training software programs for 30-45 minutes during each session (www.positscience.com). These re-training programs have been used in patients with TBI and have been shown to be effective (Fisk, Novack et al. 2002; Calvanio, Williams et al. 2004; Novack, Banos et al. 2006). Cognitive re-training will thus be individualized to each patient's cognitive level, but still be systematic, and will not need direct one-on-one supervision by a neuropsychologist.

Transcranial direct current stimulation will be delivered by trained study personnel using the saline-soaked pair of surface sponge electrodes (35 cm²) delivered by a specially developed, battery-driven, constant direct current stimulator (Fisher Wallace Cranial Stimulator, Fisher Wallace Laboratories, New York) with a maximum output of 4 mA (**Fig. 1**). FDA approval: The Cranial Stimulator is an FDA cleared device indicated for application of electrical stimulation to a patient's head to treat insomnia, depression, or anxiety. TBI subjects experience insomnia, depression and anxiety and all subjects enrolled in this study will have some combination of these problems. The purpose of this study is to understand the mechanisms behind the depression, anxiety and insomnia that patients with TBI experience. The hypothesis is that emotional dysregulation contributes to the symptoms. This device will therefore be used in alignment with FDA clearance indications. To stimulate the DLPFC, the anode electrode will be placed over F3 according to the 10-20 international system for EEG electrode placement (Fregni, Boggio et al. 2005) (**Fig.2**). The cathode will be placed over the contralateral supraorbital area.

Fig.1. FDA approved Fisher Wallace Cranial Stimulator.

[figure not shown]

Fig.2. Placement of electrodes (Rosa and Lisanby 2012).

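### The Aim 3 connectivity analysis names only a pre- versus post-treatment comparison and does not state the active-versus-sham contrast of change that its own hypothesis requires

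*Protocol*

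**What the plan says.** Section III.2 of the protocol (Data Analysis), item 3, opens with a between-arm objective: "To determine whether the tDCS intervention produces stronger functional connectivity between fronto-limbic networks compared with sham-tDCS". The hypothesis that follows concerns change from baseline compared between arms. Patients on active tDCS are expected to show "higher temporal correlation between the frontal and limbic areas compared to baseline than patients receiving sham tDCS + cognitive re-training".

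The analysis text then covers preprocessing, filtering, nuisance regressors and seeds. At group level it says three things that bear on the contrast:

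- It moves from single subjects to groups: "Individual functional connectivity maps will be registered to the MNI space and entered into group-level analyses".
- It assigns the group modelling to the FEAT software and gives no design matrix.
- It names one comparison: "Connectivity patterns pre- and post-treatment will be compared for all the seeds of interest".

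The item ends with the threshold: "Gaussian random field theory will be used for cluster-level multiple comparisons correction", at a minimum Z of 2.3 and corrected p below .05.

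Item 2 of the same section gives Aim 2 a repeated measures ANOVA of condition (two levels) by session (pre, post). Its scope is the executive attention and emotional appraisal variables.

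Sections I.3 and III.1.5 give both arms the same computerised re-training for six weeks. Section III.1.5 says of it: "These re-training programs have been used in patients with TBI and have been shown to be effective". Section I.3 schedules MRI for the TBI patients before and after treatment. Healthy controls attend visits 1 to 3 only and are not scanned.

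**The concern.** The hypothesis is a group-by-time statement, but the one comparison written for connectivity has a time term and no arm term. The sham arm is the only control in this design for whatever the two arms share between scans: re-training, the passage of time and being scanned a second time. There is no untreated group with repeat MRI to fall back on.

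A pre-post comparison pooled over arms mixes any tDCS effect with these shared changes. One run within each arm invites an informal reading, significant in active but not in sham, which does not test the difference between arms. In either case a shared change could be taken for a stimulation effect. The purpose statement says that the pilot data will support an application for further funding, so such a misreading could carry into the next study.

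**Working it through.** **Hypothesis against contrast.** Write Δ for the mean post-minus-pre connectivity of an arm.

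- Objective and hypothesis (III.2, item 3): Δ(active) − Δ(sham) > 0.
- Comparison named (same item): post versus pre, that is Δ = 0, with no arm specified.
- Group-level wording (same item): maps go to group level in FEAT, with no design matrix or contrast given.
- Condition-by-session model (III.2, item 2): the right structure, but for behavioural variables only.

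So no sentence in the protocol states Δ(active) − Δ(sham) as the test for connectivity.

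**Size of the possible misreading.** The protocol gives no power calculation or effect size for Aim 3, so there is no figure to reproduce. What follows is an illustration.

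Inputs from the protocol:
- 10 per arm (sections I.3 and III.2).
- 40 TBI patients in total (sections I.3 and II.1), which is 40 / 2 = 20 per arm. The document supports either size, so both were run.

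Assumptions:
- One scalar connectivity summary with normally distributed changes.
- Two-sided 5% tests.
- No tDCS effect.
- The same standardised pre-post change dz in both arms: 0.2, 0.5 or 0.8.

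Formulas:
- Within-arm paired t-test: noncentral t with n − 1 degrees of freedom and noncentrality dz × √n. Let u be the chance of a significant increase and p the chance of significance in either direction.
- Active significant and sham not: u × (1 − p).
- Pooled pre-post test: as for one arm, with 2n subjects.
- Between-arm test: two-sample t-test on changes, by simulation with 40,000 runs.

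Worked case, n = 10 and dz = 0.8: noncentrality 0.8 × √10 = 2.53 and critical t (9 df) = 2.262, so u = p = 0.616 to three decimals. Active only: 0.616 × (1 − 0.616) = 0.24.

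| n per arm | dz | active arm shows significant rise | active significant, sham not | pooled pre-post rise | between-arm test on change |
|---|---|---|---|---|---|
| 10 | 0.2 | 8% | 7.5% | 13% | 4.9% |
| 10 | 0.5 | 29% | 21% | 56% | 4.9% |
| 10 | 0.8 | 62% | 24% | 92% | 4.9% |
| 20 | 0.2 | 13% | 11.5% | 23% | 4.9% |
| 20 | 0.5 | 56% | 25% | 87% | 4.9% |
| 20 | 0.8 | 92% | 7% | >99% | 5.2% |

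The pre-post columns count increases only, and with no change at all they would show 2.5%. The last column counts both directions, so about half of it favours active.

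**Sensitivity of the between-arm test.** For a true standardised difference in change of 0.8, the noncentrality is 0.8 × √(n/2): 1.79 for n = 10 and 2.53 for n = 20. The normal approximation, Φ(noncentrality − 1.96), gives 43% and 72%. The t-distribution gives 40% and 69%.

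**The case against.** The strongest reply is that this is brevity. Sham is named in the opening line of the item and again in the hypothesis. Group-level analysis in FEAT could hold an arm contrast. The pre-post sentence does not say that it is pooled, within arm or the only test, and a contrast list is often left to a statistical analysis plan, which is not shown here. Much of this stands. It rules out saying that a shared effect *would* be reported as a tDCS effect; *could* is as far as the text goes. It does not remove the point. The item is detailed down to filter band and cluster threshold, and at that level it writes out a comparison that omits the arm its hypothesis depends on.

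The figures are also open to challenge, and these limits stand:

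- The shared change is assumed. The protocol calls the re-training effective but does not say that it alters resting connectivity, and it gives no retest effect.
- The chance of active only is close to p(1 − p), which cannot exceed 25%. It falls to 7% at a change of 0.8 with 20 per arm, so no single scenario should be quoted alone.
- The planned analysis is voxelwise and cluster-corrected, and percentages for one uncorrected scalar do not transfer to it.

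Finally, this is a pilot with a sample that the protocol itself describes as arbitrary. That limits the weight of the point. Even so, Aim 3 states a directional hypothesis and a corrected significance threshold.

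**Conclusion.** The point holds as a mismatch between hypothesis and stated contrast. Aim 3 concerns the active-minus-sham difference in change, the text names only pre versus post, and no other analysis in the protocol covers connectivity between arms.

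A reader might go further and infer that the imaging aim cannot separate tDCS from training, or that the investigators intend to compare significance across arms. The protocol supports neither. The randomised sham arm and both scans supply the data for the right test, the objective names sham, and no rule based on significant in one arm and not the other is written anywhere.

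Under the assumed range of shared change, with no tDCS effect, a significant rise in the active arm would appear in 8% to 62% of trials with 10 per arm and 13% to 92% with 20. The pattern of active significant and sham not would appear in 7.5% to 24% and 7% to 25%. The between-arm test stays near 5% throughout. These figures show direction and rough scale only.

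**What to change.** Replace the pre-post sentence in section III.2, item 3, with text such as:

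> For each subject and for all the seeds of interest, a post-minus-pre connectivity difference map will be computed. The Aim 3 test is active versus sham on these difference maps (group-by-time), with the stated cluster-level correction. Within-arm pre-post maps are descriptive.

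This keeps the scope over all seeds and the existing threshold. It costs a short text change and a different group-level design matrix, with no new scans, visits or patients. The price is sensitivity: at a standardised difference in change of 0.8, power for a scalar summary is roughly 40% with 10 per arm and about 70% with 20. The report should therefore give the estimated between-arm difference with its interval and should not read a non-significant result as no effect.

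### The cluster-corrected p < .05 for connectivity covers one seed's map only, but Aim 3 repeats the comparison over an open list of seeds and names no lead seed

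*Protocol*

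**What the plan says.** The relevant text is Protocol section III.2 (Data Analysis and Data Monitoring), Data Analysis, item 3.

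- **Hypothesis.** It is single and directional: "Patients receiving tDCS + cognitive re-training will show higher temporal correlation between the frontal and limbic areas compared to baseline than patients receiving sham tDCS" plus re-training.
- **Seeds.** "Average resting state time series will be obtained for all the seeds of interest, particularly in the" "cingulate motor cortex, and dorsolateral premotor cortex". Two regions are named, and the wording presents them as examples from a longer list.
- **Unit of analysis.** "FSL FEAT will be employed to find the brain voxels that correlate with the seed time series in each subject". Each seed therefore yields its own voxel map per subject, and these maps go into group-level analysis.
- **Scope of the comparison.** "Connectivity patterns pre- and post-treatment will be compared for all the seeds of interest".
- **Error control.** "Gaussian random field theory will be used for cluster-level multiple comparisons correction (minimum $Z > 2.3$; $p < .05$, corrected) for the resting state analyses".

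The section gives no number of seeds, no primary seed, no order of testing and no rule for combining results over seeds. It also does not say whether the corrected level is meant per seed map or for the set of maps.

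**The concern.** Cluster-level random field inference answers one question: given this statistic map, how likely is a cluster this large anywhere in it if there is no effect? It accounts for searching over the voxels of that map. It does not account for running the search again on a second map from a different seed.

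Here several maps serve one hypothesis, and nothing says which of them decides it. Followed as written, the plan lets a significant cluster from any one seed be reported as corrected support for the claim that tDCS strengthens fronto-limbic connectivity. The open list adds a second problem: seeds can be added, or one can be put forward, after the maps have been seen. The study is meant to supply pilot data for a funding application, so a chance finding presented as corrected could steer the next trial toward the wrong target.

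**Working it through.** **Inputs**

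- Level per seed map: α = .05 after cluster correction (section III.2, Data Analysis, item 3).
- Number of seed maps, k: at least 2, from the two named regions. The true number is not stated.
- Assumptions: random field correction attains its nominal level within each map, each seed contributes one test, and no seed has a true effect. The correlation between the seeds' test statistics is not in the document, so a range is shown.

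**Step 1: the plan's own figure.** With one seed and one contrast, the chance of a false-positive map is

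1 − (1 − .05)^1 = .05.

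The stated level is met for a single map.

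**Step 2: the two named seeds, independent maps.**

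1 − (1 − .05)^2 = 1 − .9025 = .0975, or 9.75%.

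**Step 3: upper bound under any dependence.** The Bonferroni inequality gives at most k × .05. For k = 2 that is 2 × .05 = 10%.

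**Step 4: correlated maps.** Each seed's test was represented by a Gaussian statistic with a 5% upper tail, with common correlation ρ between the two seeds (simulation, 500,000 draws per value).

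| ρ (assumed) | Chance of at least one false-positive map, k = 2 |
|---|---|
| 0.3 | 9.3% |
| 0.5 | 8.8% |
| 0.7 | 8.0% |
| 0.9 | 6.8% |
| 1.0 | 5.0% |

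In this model, positive correlation reduces the excess but removes it only when the two statistics are perfectly dependent.

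**Step 5: the open list.** The general bound, k × .05, rises with every seed added. The document does not fix k, so it does not fix a bound.

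**Step 6: check of the remedies.** One pre-named seed returns to Step 1, at 5%. Two seeds at .05 / 2 = .025 each give 1 − (1 − .025)^2 = 1 − .950625 = .0494, or 4.94%, if independent, and at most 2 × .025 = 5% under any dependence.

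**The case against.** **The Protocol never promises 5% for Aim 3 as a whole.** This stands. The sentence attaches the level to a cluster-level correction for the resting-state analyses. A reader might infer that a stated Aim-wide 5% is broken, but the text makes no such statement. What can be said is that the rule works within a map, that it follows directly on a sentence extending the comparison to all seeds, and that nothing tells the reader how far the correction reaches.

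**The inflation could be made to look much larger.** A reader might infer a risk several times 5%. Four independent maps would give 1 − .95^4 = 18.5%, and eight would give 1 − .95^8 = 33.7%. The document does not support those counts. It names two regions and does not mention seeds in each hemisphere or any specific further seed. Nor does it help to double the count by treating increases and decreases as separate tests. The hypothesis is directional, so a decrease could not be reported as support for it, and a two-sided 5% test already covers both directions.

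**The details belong in an SAP.** This stands in part. An SAP, which was not available here, could close the seed list or add an adjustment over seeds. But the Protocol did not defer the matter. It fixes the method, the cluster threshold, the level and the scope itself, and it writes the seed list as open.

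**This is a pilot.** Section III.2 calls the sample size small and arbitrary and gives 10 per group. Strict error control over seeds is debatable in such a study, and a smaller α per map would cost power that is already scarce. This limits the weight and is a reason to prefer naming one seed over dividing α. It does not justify leaving the choice of seed open until the results are known.

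**Conclusion.** The point holds with modest weight. The cluster correction controls error within one seed's map, while the comparison is repeated over an unspecified number of seeds for a single directional hypothesis. For the two named seeds, the chance of at least one false-positive map is up to about 10%: 9.75% if the maps are independent, and about 7 to 9% for correlations from 0.9 down to 0.3. Beyond two seeds the document sets no limit.

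These figures assume that the within-map correction performs at its nominal level, that there is one test per seed, and that no seed has a true effect. The correlations are assumed. The conclusion is that the reach of the correction and the deciding seed are left undefined. It is not that a declared Aim 3 error rate has been violated.

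**What to change.** In section III.2, Data Analysis, item 3, before any post-treatment map is seen:

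1. Name one seed, and name the tDCS-versus-sham difference in pre-to-post change, in the hypothesised direction, as the Aim 3 test at cluster-corrected p < .05.
2. Report the maps from all other seeds as exploratory.
3. State that corrected means corrected over the voxels within one map, not over seeds.

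This takes two or three sentences, leaves the threshold for the named seed at .05, and removes any selection among maps. The cost is that a finding from another seed could only suggest a hypothesis for later work.

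If both named seeds are to remain Aim 3 tests, close the list at those two and use cluster-corrected p < .025 for each. That costs some power per map. The loss is not quantified here because the Protocol gives no effect size or variance for connectivity.
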